After approximately eight hours, if all medical parameters are acceptable and the subject is alert, ambulatory and emotionally stable, the session will end. During the last 30 - 60 minutes of the session a designated support person (a spouse, partner, relative or friend) may join in this meeting. After the researchers leave (when they have judged the participant to be emotionally and medically stable), the participant will spend the rest of the evening and night at [name]'s office where the MDMA-assisted therapy session will take place. The office is located right next to the house of [name]. He will check on the participant before he leaves for the night. He is available on all times during the night following the experimental session if requested to do so by the participant or the designated support person. He will evaluate whether the participant is in need of any further medical intervention and will assist the participant in coping with increased psychological distress if necessary. Throughout the study, [name] will remain available to participants via 24-hour cellular phone.

Participants will be encouraged to use much of the time for rest and for a period of reflection and integration in a quiet atmosphere. The participant may request that their designated support person, described above remain with them during the night, pending approval from [name] after he has met this support person and has discussed the possible advantages and pitfalls with the study subject.

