2.8.5.2. Details of Non-Drug Psychotherapy 24 Hours Post-Experimental Session

The scheduled sixty to ninety-minute therapy session will take place in the morning after the experimental session. After this psychotherapy session, a person previously selected by the subject will provide a ride home. If the participant is unable to locate an individual willing or able to take him or her home, or if the designated person is unable to assist the participant due to unforeseen events, the investigators will assist the participant in finding an alternative means of returning home.

The therapist-investigators and the participant will discuss the experimental session and any material that arose during the session and will seek to integrate this material. The therapist-investigators will

assist the participant in addressing any residual psychological distress he or she is experiencing. The participant and both investigators will complete measures of their beliefs concerning the participant's condition assignment. The non-drug psychotherapy session can also serve as an opportunity for the therapist-investigators to gather information about the effects of MDMA on the participant in an unstructured manner.

Starting on the day of the non-drug psychotherapy session following each experimental session, one of the investigators will contact the participant via telephone on a daily basis for one week. The investigators will use clinical judgment to assess the participant's psychological well-being during this period of time. If there are any indications of continuing anxiety or distress, the investigators may arrange to work on reducing the distress at a specially scheduled non-drug therapy session, through continuing contact, or at the next regularly scheduled non-drug therapy session. The participant may also initiate contact with the investigators at any time throughout the study.

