The potential for destabilizing psychological distress will be minimized by excluding people who might be more vulnerable to it (such as people diagnosed with bipolar affective disorder - 1 or with psychotic disorders), by preparing people before the experimental session, by creating an atmosphere of trust during the experimental session, by close monitoring, by daily contact with subjects for the period of a week after the experimental session, and by providing non-drug integrative psychotherapy sessions. Participants will remain at the research facility for the night after each experimental session. The investigator will be able to attend to the participant if there is a need to deal with continued psychological distress.

If, by the end of the 6 to 8 hour experimental session, the participant is still severely agitated or experiencing great psychological distress, the following measures will be taken:

- If a participant is anxious, agitated, in danger of any self harm or is suicidal at the end of the experimental session, the investigators will remain with the participant for at least two more hours. During this time, the investigators will employ affect management techniques described in the treatment manual draft (Ruse et al. 2005), will talk with the participant to help him or her gain cognitive perspective of their experiences, and will help them implement the self soothing and stress inoculation techniques they were taught in the introductory sessions. If this situation should occur at the end of one of the ninety-minute follow-up sessions at least one of the investigators will be available to stay with the participant for at least two additional hours.

- If a participant remains severely anxious, agitated or in danger of self harm or suicide, or is otherwise psychologically unstable at the end of this two hour stabilization period, the principal investigator may undertake one of two options:

A. A designated support person will stay with the participant until the time of his or her appointment with investigators the next day. The investigators will then meet with the participant daily until the period of destabilization has passed. At any time during this process, [name] may make the clinical judgment to proceed to option B.

B. Hospitalization for stabilization

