Participants hospitalized after a severe panic reaction will be suspended from study participation until after recovery or stabilization, at which time the investigator will carefully evaluate the participant's emotional status. If this response occurs during the first experimental session, the investigator may elect to forego the further experimental sessions and drop the participant from the study. This decision will be made after discussion with the ethics committee and any other appropriate regulatory agencies. For those participants engaged in an on-going therapeutic relationship, we will actively involve their outside therapists in the management of any psychiatric complications of treatment.

In the event of a participant's experiencing severe, persisting emotional distress, such as panic attacks, severe generalized anxiety or insomnia following an experimental session, the investigator may prescribe a benzodiazepine or zolpidem as a “rescue medication.” If a participant should become psychotic or suicidal, arrangements will be made for him or her to be admitted to the nearest inpatient psychiatric facility of their choice. Residual symptoms will be addressed during the frequent follow-up psychotherapy visits with the investigators.

Any participant who develops mania or psychosis will not be given a further MDMA session and will receive appropriate psychiatric treatment.

Hyperthermia:

If temperature rises more than 1° C, attempts will be made to lower it by removing blankets and layers of clothing, decreasing the ambient temperature and, if necessary, directing a fan toward the participant. If at any time the temperature rises more than 1.5° C above baseline despite these efforts, ice packs will be used, blood will be drawn for stat CBC, electrolytes, BUN, creatinine, glucose, CPK, PT, PTT, platelets and liver enzymes, and urine will be collected for urinalysis. If there are significant abnormalities in these tests, if the temperature continues to rise, or if an elevated temperature is associated with delirium or muscle rigidity the participant will be transferred to the nearest ICU. If, during the first or second experimental session, a participant's temperature rises more than 1 ° C. and does not rapidly come down after the above adjustments have been made in blankets, clothing, ambient temperature and ventilation, then that participant will not be given any subsequent experimental sessions.

Dehydration:

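### After the two-hour stabilisation period, one safety rule lets a suicidal participant stay out of hospital and another under the same heading requires admission

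*Protocol*

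**What the plan says.** All the governing text is in Protocol section 2.8.8, under Psychological Toxicity.

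- **First step.** "If a participant is anxious, agitated, in danger of any self harm or is suicidal at the end of the experimental session", the investigators stay for at least two more hours and use affect-management techniques. The same bullet extends this to later visits: "If this situation should occur at the end of one of the ninety-minute follow-up sessions", at least one investigator will be available for at least two further hours.
- **Second step.** "If a participant remains severely anxious, agitated or in danger of self harm or suicide, or is otherwise psychologically unstable" when those two hours are over, the principal investigator may take one of two courses. Under option A, "A designated support person will stay with the participant until the time of his or her appointment with investigators the next day", followed by daily meetings with the investigators until the episode has passed. Option B is hospitalisation. While option A is running, the investigator "may make the clinical judgment to proceed to option B" at any time.
- **Admission rule.** Further on, the protocol states: "If a participant should become psychotic or suicidal, arrangements will be made for him or her to be admitted to the nearest inpatient" (a psychiatric facility, chosen by the participant).

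Two other sections bear on the setting. Section 2.8.5.1 has the participant sleep at the office, next to the investigator's house, and says of the investigator: "He is available on all times during the night following the experimental session", on request; it also gives 24-hour telephone access throughout the study. Section 2.8.5.2 covers the day after: "After this psychotherapy session, a person previously selected by the subject will provide a ride home".

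The SAP does not address the management of suicidality.

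**The concern.** For a participant still in danger of suicide after two hours, the stepped pathway makes admission optional and the later sentence makes it the required course. An investigator who chooses option A follows one rule and breaks the other. Two investigators could manage the same participant differently and each point to the protocol in support.

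What is at stake is participant safety and the classification of conduct. The less strict rule allows a suicidal participant to remain outside hospital with a companion for whom the protocol sets no training requirement. SAP section 6.2 has a deviation category for procedures not carried out as the protocol prescribes; under the present text, choosing option A for a suicidal participant both is and is not such a deviation.

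**Working it through.** The plan states no figure on this point, so the check compares the two rules directly.

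| | Stepped pathway | Admission rule |
|---|---|---|
| Who | Still in danger of self harm or suicide, or otherwise unstable | Becomes psychotic or suicidal |
| When | After the two-hour period | No time window stated |
| Force | Discretionary (*may*) | Directive (*will*) |
| Action | A: support person, then daily meetings; or B: hospitalisation | Arrangements for inpatient psychiatric admission |

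Applied to a participant who is suicidal at session end and still so two hours later:

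- Option B: the pathway is met and the admission rule is met.
- Option A: the pathway is met and the admission rule is not.

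Four ways of reconciling the rules were then tried.

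1. **Different states.** Being in danger of suicide might be milder than being suicidal. Neither term is defined. The pathway's first bullet names the participant who is suicidal, and its second covers those who remain in danger, so the two groups overlap.
2. **Different times.** The admission rule might cover only later onset. It sets no such limit, and the end of the two-hour period is itself after an experimental session. The pathway's first bullet also reaches the ninety-minute follow-up sessions, so the two rules do not divide neatly into session night and afterwards.
3. **An order of precedence.** No cross-reference, exception or ranking appears in either document. Other text on suicide risk, exclusion criterion 9 in section 2.7.2, concerns eligibility only.
4. **Escalation.** Moving from A to B is also discretionary and has no criterion tied to suicidality. It permits admission without requiring it.

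Option A's safeguards are real: daily meetings, escalation at any time and the investigator next door. The next-door night cover, however, is stated only for the night after an experimental session. After the day-after session the plan is a ride home, and section 2.8.8 does not say where option A would then take place; 24-hour telephone contact remains.

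**Occasions.** From sections 2.5 and 2.8.1, with 12 participants, three sessions each, and 8 full-dose and 4 low-dose:

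- Stage 1 experimental sessions: 12 × 3 = 36
- Full dose: 8 × 3 = 24
- Low dose: 4 × 3 = 12

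The follow-up visits and the open-label Stages 2 and 3, which use the same session procedures, are additional. These are occasions on which the rules could be called on; they say nothing about how often that would happen.

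The conflict concerns suicide only. The admission rule does not mention self harm, so the choice between A and B for self harm without suicidality contradicts nothing.

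**The case against.** The strongest reply is that the pathway is specific and the admission rule general. The pathway opens with the end of the experimental session and deals with someone who has not settled. The admission sentence follows one on persisting distress after a session, speaks of a participant *becoming* suicidal, and pairs suicidality with psychosis. Letting the specific rule govern session end and the general rule govern later onset would give both a role. That reading is reasonable, but the reader has to supply it. It would also let the laxer rule override a directive to admit, which ought to be an explicit decision.

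A second reply is that the admission duty is soft: arrangements are to be made, with no deadline, so the two hours of stabilisation do not breach it and option A could be cover while a bed is found. The point about the two hours is right, and they are not criticised here. The rest fails on the text: option A is written as a complete alternative, with daily meetings until the episode passes, and not as a bridge to admission.

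Third, the reach to follow-up sessions is less firmly written. The sentence on those visits speaks only of an investigator staying on, and option A assumes a next-day appointment, whereas integrative sessions are weekly. The A/B choice reaches those visits only through its reference back to the two-hour period. The conflict at the end of an experimental session does not depend on this.

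Finally, people presenting a serious suicide risk are excluded at entry, immediate hospitalisation is always open to the investigator, and the count of 36 adds little. All of that stands. It bears on how often the problem would arise and does not decide which rule applies when it does.

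**Conclusion.** The contradiction holds. For a participant still suicidal after the two-hour period, option A complies with one rule in section 2.8.8 and breaches another, and neither document ranks them. This rests on the ordinary meaning of undefined terms and on the absence of any time limit in the admission rule.

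Its size cannot be expressed as expected cases, because no rate of suicidality is given. Sample size, error rates, power and the efficacy analyses are untouched. It should be fixed because it is a clear conflict in a suicide-safety rule with a small remedy. The SAP describes conduct in the past tense, so the correction now matters chiefly for the protocol text, for classifying deviations and for any reuse of this safety section.

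**What to change.** In section 2.8.8, restrict option A to participants who are anxious, agitated or otherwise unstable but not in danger of suicide. State that a participant judged suicidal at the end of the two-hour period, whether after an experimental or a follow-up session, is admitted under the existing admission rule. The choice between A and B can stay for danger of self harm without suicidality.

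If the sponsor and ethics committee prefer to keep discretion for suicidal participants, amend the admission rule to say so. Either change removes the conflict; the first follows the protocol's own stricter standard.

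The cost is protocol wording only. The downside of the first version is one or more admissions that might have been avoided.

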2.7. Participants

The first twelve participants who meet all inclusion criteria without meeting any exclusion criteria will be admitted to the study. Participants enrolled in the study who withdraw during treatment or who the researchers decide for any reason should not continue in the study (“drop-outs”) will be replaced. Participants will be recruited for the study by call for referral from specialized institutions such as trauma advice and counseling centers (outpatient clinics for psychotraumatology), as well as psychiatrists and psychotherapists in private practice (see enclosed).

2.7.1. *Inclusion Criteria*

Participants who meet the following criteria will be considered for inclusion in this study:

1. Participants must meet DSM IV criteria for current PTSD (within the past 6 months) in response to a traumatic experience. An individual would not be excluded if she or he experienced more than one traumatic event. Participants must have a CAPS score of 50 or higher, indicating moderate to severe PTSD symptoms.
2. They must have had at least one unsuccessful attempt at treatment for PTSD. Treatments include psychotherapy and pharmacotherapy. Pharmacotherapies may include selective serotonin uptake inhibitors (SSRIs). Psychotherapeutic treatments may include, but are not limited to cognitive-behavioral therapy (including exposure therapy), stress inoculation training, including anxiety management, and insight-oriented psychotherapy (Foa et al. 2003; Jaycox et al. 2002; Krupnik 2002; Resick and Schnicke 1992). Treatment will be deemed unsuccessful if the participant continues to meet criteria for current PTSD following the treatment.
3. Participants may also meet criteria for a mood disorder (except bipolar affective disorder, see exclusions) and for other anxiety disorders. The inclusion of people with other mood and anxiety disorders is essential because recent literature (Brady et al., 1994; Faustman & White, 1989) indicates the marked frequency of the co-existence of other psychiatric disorders among patients with PTSD.
4. Participants must be at least 18 years old.
5. Participants must be willing to commit to medication dosing, therapy sessions, and follow-up sessions and to complete evaluation instruments.

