1. Participants who appear at imminent risk for trauma and victimization as assessed by information gathered during the screening will not be eligible for study participation.
2. Women who are pregnant or nursing, or of child bearing potential and not practicing an effective means of birth control.
3. Participants with a history of or current primary psychotic disorder or bipolar affective disorder type 1.
4. Participants with dissociative identity disorder, or an eating disorder with active purging or borderline personality disorder.
5. Participants with evidence or history of significant hematological, endocrine, cerebrovascular, cardiovascular, coronary, pulmonary, renal, gastrointestinal, immunocompromising, or neurological disease, including seizure disorder. (People with hypothyroidism who are on adequate and stable thyroid replacement will not be excluded).
6. Participants with uncontrolled hypertension, peripheral vascular disease, hepatic disease (with or without abnormal liver enzymes), or history of hyponatremia or hyperthermia.
7. Participants weighing less than 50 kg or more than 105 kg.
8. Patients reporting prior use of "Ecstasy" more than 5 times or at any time within the previous 6 months.

9. Participants who would present a serious suicide risk or who are likely to require hospitalization during the course of the study.
10. Participants requiring ongoing concomitant therapy with a psychotropic drug.
11. Participants meeting DSM-IV criteria for substance abuse or dependence for any substance save caffeine or nicotine in the past 60 days.
12. Any participant who is not able to give adequate informed consent. Participants in need of special protection such as minors; participants without the legal ability to act; participants who lack sufficient understanding or capacity to make or communicate responsible decisions concerning themselves by reason of mental illness, mental deficiency, physical illness or disability, advanced age or other cause (incapacitated persons).

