2.8.6. Open Label Continuation for Active Placebo Patients ("Stage 2")

After each participant completes all outcome measures on the session scheduled 3 weeks after the third experimental session (T2), the participant will have a 30-minute meeting with the principal investigator. During this meeting, the blind will be broken for the individual participant while retaining the blind for the independent assessor. If a participant had received the Low (25 mg followed 2.5 hours later by 12.5 mg) dose of MDMA during the course of the study, she or he would be offered an opportunity to enroll in the open label continuation of the study, referred to as Stage 2. He or she would give written informed consent to take part in this second stage of the study, with consent given separately from the initial consent. If the participant consents to take part in Stage 2 of the study, he or she would receive the Fully Active dose of MDMA (125 mg followed 2.5 hours later by 62.5 mg) during three experimental sessions scheduled two to four weeks apart. Outcome measures administered three weeks after the third experimental session will serve as baseline measures for Stage 2. The participant would undergo one preparatory non-drug psychotherapy session 1 to 2 weeks prior to the first experimental session, and he or she would receive non-drug psychotherapy follow-up sessions according to the same schedule described for the active placebo controlled study. Procedures for non-drug psychotherapy sessions, experimental sessions, weekly telephone contact and outcome measure administration will be the same as those employed in the first stage of the study.

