In order to avoid dehydration, participants will be encouraged to drink 750 - 1500 ml. of Gatorade or a similar electrolyte-containing fluid during the session depending on their size, level of activity and body temperature.

Hyponatremia:

Participants will be given electrolyte solutions such as Gatorade instead of water in order to decrease the likelihood of dilutional hyponatremia. They will not be allowed to drink more than 3 L. of fluids over the course of the experimental session, and fluid intake will be spread out appropriately during the session. If there are any signs or symptoms of hyponatremia such as confusion, vomiting, myoclonus or ataxia, a stat serum sodium will be drawn and fluids will be withheld until the results are obtained. If the serum sodium is less than 125mEq/L, serum and urine osmolality and sodium will be measured, If serum sodium is less than 125mEq/L, serum and urine osmolality and sodium will be measured, and the subject will be transported to the ICU.

If a participant had low serum sodium during the experimental session and exhibited signs of clinically significant hyponatremia, then the principal investigator will not enroll the participant in any subsequent experimental sessions unless, in the clinical judgment of the investigators, further fluid restriction during the second experimental session would be a sufficient means of preventing hyponatremia.

Liver toxicity:

Liver enzymes will be measured as part of the initial screening visit. Volunteers with pre-existing abnormalities will be excluded from the study. If a participant exhibits signs of liver toxicity after an experimental session, then he or she will not receive a subsequent experimental session.

Neuropsychological toxicity:

Psychological and neurological status will be clinically monitored by the therapists during MDMA sessions and during therapy sessions at frequent intervals thereafter. If, on clinical examination after each experimental session, a participant is found to have cognitive deficits that persist for more than two weeks, this participant will not be given a subsequent experimental session.

Abuse and dependence:

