4.0 Study design

The study followed a randomized, active placebo-controlled, double-blind design, with subjects, psychotherapists and independent raters blinded to participant condition. Twelve subjects with treatment-resistant PTSD were randomly assigned after baseline assessment to receive either full dose of 125 mg MDMA followed by a supplemental dose of 62.5 mg MDMA administered 2.5 h

later, or to an active placebo dose of 25 mg MDMA followed by 12.5mg MDMA 2.5h later. Participants underwent three sessions of MDMA-assisted psychotherapy scheduled to occur three to five weeks apart, 1 non-drug-psychotherapy session 24 h after each MDMA-session and 2-4 weekly integrative psychotherapy sessions after each MDMA session. PTSD symptoms were assessed by an independent rater once prior to MDMA-assisted psychotherapy, three weeks after the second MDMA-assisted session, three weeks after the third experimental session. After unblinding, active placebo participants had the opportunity to take part in an open-label continuation of the study, referred to here as "Stage 2." Data gathered three weeks after the third experimental session was treated as the baseline for Stage 2, and outcome measures were administered three weeks after the second and third experimental session. Originally outcome measures would also be given two, six and twelve months after the third experimental session, but the six-month evaluations were discontinued after January 2009 in line with the Amendment 5 of the protocol. Participants receiving the full dose in either Stage 1 or Stage 2 who did not show significant improvement in PTSD symptoms were offered the opportunity to take part in an open-label continuation of the study, "Stage 3", consisting of two additional MDMA sessions. During these sessions, they could receive 125 mg followed 2.5 hours later by 62.5 mg MDMA or a 20% larger dose of 150 mg MDMA, followed by a supplemental dose of 75 mg administered 2.5 hours later, unless contraindicated by safety parameters. Outcome measurements gathered at 2 months after the third experimental session will serve as baseline measures for Stage 3. Stage 3 was also cancelled in line with Amendment 5. Of the 12 participants who completed the study, only three participants underwent Stage 3.

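### The hyperthermia stop rule covers only sessions 1 and 2, so an uncontrolled temperature rise in session 3 does not automatically bar Stage 2 or Stage 3

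*Protocol*

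**What the plan says.** The hyperthermia paragraph of Protocol 2.8.8 has two parts.

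- **Acute management**, in every session: active cooling once the rise exceeds 1 °C, then a clause that begins "If at any time the temperature rises more than" and goes on, above 1.5 °C, to ice packs and urgent laboratory tests, with ICU transfer for defined complications.
- **A bar on later dosing**: a participant whose rise exceeds 1 °C and is not quickly reversed receives no further experimental sessions. This part is limited by the words "If, during the first or second experimental session".

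Stage 1 has three sessions (2.8.1), Stage 2 has three (2.8.6) and Stage 3 has two (2.8.7). Stage 2 is offered to Low Dose participants after unblinding, with separate consent. Stage 3 is offered after an insufficient response to the full dose in Stage 1 or Stage 2, again with separate consent. Neither section makes entry depend on temperature in earlier sessions.

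Three other texts touch on the point. Section 2.7 allows withdrawal of anyone "who the researchers decide for any reason should not continue in the study". Exclusion criterion 6 in 2.7.2 lists "history of hyponatremia or hyperthermia". SAP 4.0 says the Stage 3 doses could be given "unless contraindicated by safety parameters".

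**The concern.** Within a single three-session stage, sessions 1 and 2 are exactly those followed by another dose, so the wording is complete for Stage 1 taken alone. The open-label stages change that: session 3 is no longer necessarily the last exposure. The rule was not extended to match, so the protocol's own threshold for withholding the drug does not bind at the two points where a participant moves to another stage.

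What is at stake is patient safety. The next dose is never planned to be lower than the one that produced the rise, and Protocol 4.6.1 says that hyperthermia may depend on dose. The Stage 1 efficacy comparison is not affected.

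**Working it through.** The plan gives no figure to reproduce. The check compares the stop rules and then counts sessions.

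**1. The stop rules in 2.8.8 side by side**

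| Trigger | Session limit | Consequence |
|---|---|---|
| Blood pressure or heart rate | none | mandatory bar |
| Mania or psychosis | none | mandatory bar |
| Liver toxicity | none | mandatory bar |
| Persisting cognitive deficit | none | mandatory bar |
| Hyperthermia | first or second session | mandatory bar |
| Hyponatremia | second session named in the exception | default bar, with an exception by judgment |
| Hospitalisation after severe panic | first session named | discretionary |

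The hyponatremia exception applies if the investigators judge that "further fluid restriction during the second experimental session would be a sufficient means of preventing hyponatremia". The panic text reads "If this response occurs during the first experimental session, the investigator may elect to forego the further experimental sessions". Hyperthermia is therefore the only mandatory bar tied to particular sessions, and no reason is given.

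**2. Which sessions can be followed by another dose**

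Every session on a path except the last can be followed by another.

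- Stage 1 to 3: 3 + 2 = 5 sessions, of which 4 can be followed by another.
- Stage 1 to 2: 3 + 3 = 6 sessions, of which 5.
- Stage 1 to 2 to 3: 3 + 3 + 2 = 8 sessions, of which 7.

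**3. How many of these the rule misses**

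The text does not say whether the numbering restarts in each stage. Section 2.8.6 supports a restart, because it says that procedures for "experimental sessions, weekly telephone contact and outcome measure administration will be the same as those employed in the first stage of the study". That reading favours the plan, and the conclusion uses it.

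| Path | Numbering restarts | Counted once over the study |
|---|---|---|
| Stage 1 to 3 | 1 of 4 | 4 − 2 = 2 of 4 |
| Stage 1 to 2 | 1 of 5 | 5 − 2 = 3 of 5 |
| Stage 1 to 2 to 3 | 2 of 7 | 7 − 2 = 5 of 7 |

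With a restart, the uncovered sessions are session 3 of Stage 1 and, on the longest path, session 3 of Stage 2 as well. Session 3 of Stage 1 is uncovered under either reading.

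**4. Dose step after the uncovered session** (cumulative doses from Table 1 in 2.8.1)

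- Into Stage 2: 187.5 / 37.5 = 5.0 (initial doses 125 / 25 = 5.0).
- Into Stage 3: 187.5 / 187.5 = 1.0, or 225 / 187.5 = 1.2.

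**5. Reach**

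Up to 4 participants could enter Stage 2, since 4 of 12 are allocated to the Low Dose (2.8.1). Three entered Stage 3 before it was cancelled (SAP 4.0). These are stage entries, not temperature events. The documents give no rate for a qualifying rise, so no event count is estimated.

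**The case against.** The strongest reply is that this is a drafting slip with little practical consequence. Harm requires a first qualifying event in session 3, progression to another stage, and failure of every other safeguard. Protocol 4.6.1 considers hyperthermia very unlikely in this setting, and 4.2 reports only slight temperature increases in controlled studies and expects minimal effect at 25 mg. The trigger is low, and a dangerous rise meets the acute rules in every session.

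A physician is also present at each transition. The investigator meets the participant before any Stage 2 offer (2.8.6). The 2-month follow-up, which is the Stage 3 baseline, includes a medical examination (4.6.2). Stage 3 eligibility and dose rest on clinical judgment (2.8.7). Each later stage needs fresh consent, and criterion 6 could be read as applying again then. Finally, the SAP refers to Amendment 5, which this protocol text does not reflect, so 2.8.8 may have been revised later.

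Most of this stands as a limit on size. It does not close the gap. The acute rules do not govern later dosing. The meeting, the examination and the general power to withdraw a participant are either discretionary or silent on temperature. Criterion 6 is written for prospective participants, its re-application is not stated, and a rise just over 1 °C need not count as a history of hyperthermia. The SAP clause defines no parameter and concerns Stage 3 only. A possible later revision cannot be confirmed from the documents.

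**Conclusion.** The concern holds: an uncontrolled rise in session 3 of Stage 1 or Stage 2 triggers no automatic bar on the next stage. On the reading more favourable to the plan, the gap covers 1 of 4, 1 of 5 or 2 of 7 sessions that can be followed by another dose.

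The more plausible route is from full dose to Stage 3, at the same or a 20% larger dose. The fivefold step into Stage 2 is larger, but it requires an uncontrolled rise at 25 mg followed by 12.5 mg. The dose ratios assume that the supplemental dose is taken both times; the ratios of initial doses are the same. Cancelling Stage 3 closes that route and leaves the one into Stage 2.

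The probability is low and few participants are exposed, but a stop rule is written for the unlikely case. It should be fixed, because the correction is cheap and makes the rule serve its own purpose.

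**What to change.** In the hyperthermia paragraph of 2.8.8, replace the opening condition with *during any experimental session in any stage*, and extend the consequence with *including in Stage 2 or Stage 3*.

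This changes one phrase and adds one clause. Temperature is already measured in every session, and the later stages use the same session procedures, so no new measurement is needed. The one downside is that a participant with a session-3 event loses access to an open-label stage. The protocol already accepts the loss of later sessions after an event in session 1 or 2.
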